### 6.3 Dose Modifications for Infusion-Related Reactions

For patients who have allergic or acute infusion reactions to nivolumab or ipilimumab, therapy modifications based on grade should be as follows.

Grade (CTCAE v.5) Infusion Reaction	Action
Grade 1	
 
• Monitor patient until recovery from symptoms; infusion rate may be slowed.
 
• If the infusion is interrupted, then restart the infusion at 50% of the original infusion rate when symptoms resolve; if no further complications ensue after 30 minutes, the rate may be increased to 100% of the original infusion rate. Monitor patient closely.
 
 
The following prophylactic premedications are recommended for future infusions: diphenhydramine 1 mg/kg with max 50 mg (or equivalent) and/or acetaminophen 10-15 mg/kg (max 1000 mg) at least 30 minutes before additional nivolumab or ipilimumab administrations, slowing infusion rate as above.

Grade 2	
 
• Stop infusion, begin an IV infusion of normal saline, and treat the subject with diphenhydramine 1 mg/kg with max 50 mg IV (or equivalent) and/or acetaminophen 10-15 mg/kg (max 1000 mg); remain at bedside and monitor patient until resolution of symptoms. Corticosteroid or bronchodilator therapy may also be administered as appropriate.
 
• If the infusion is interrupted, then restart the infusion at 50% of the original infusion rate when symptoms resolve;
 

	
if no further complications ensue after 30 minutes, the rate may be increased to 100% of the original infusion rate. Monitor patient closely.
 
 
• If symptoms recur, then no further nivolumab or ipilimumab will be administered at that visit. Administer diphenhydramine 1 mg/kg with max 50 mg IV (or equivalent), and remain at bedside and monitor the patient until resolution of symptoms.
 
 
The following prophylactic premedications are recommended for future infusions: diphenhydramine 1 mg/kg with max 50 mg IV (or equivalent) and acetaminophen (10-15 mg/kg, max 1000 mg) should be administered at least 30 minutes before additional nivolumab or ipilimumab administrations. If clinically indicated, corticosteroids (recommended dose: 1-2 mg/kg/day methylprednisolone IV or equivalent) may be used.

Grade 3 or 4	
 
• Immediately discontinue infusion of nivolumab/ipilimumab.
 
• Begin an IV infusion of normal saline, and treat the subject as follows. Recommend bronchodilators, epinephrine 0.2 to 1 mg of a 1:1,000 solution for subcutaneous administration or 0.1 to 0.25 mg of a 1:10,000 solution injected slowly for IV administration, and/or diphenhydramine 1 mg/kg with max 50 mg IV with 1-2 mg/kg/day methylprednisolone IV (or equivalent), as needed.
 
• Patient should be monitored until the investigator is comfortable that the symptoms will not recur.
 
• Nivolumab/ipilimumab will be permanently discontinued.
 
 
Investigators should follow their institutional guidelines for the treatment of anaphylaxis. Remain at bedside and monitor patient until recovery from symptoms. In the case of late-occurring hypersensitivity symptoms (e.g., appearance of a localized or generalized pruritis within 1 week after treatment), symptomatic treatment may be given (e.g., oral antihistamine, or corticosteroids).
 
Please note that late occurring events including isolated fever and fatigue may represent the presentation of systemic inflammation. Please evaluate accordingly.

6.4 **Dose Modifications for Skin Rash and Oral Lesions**

Skin Rash and Oral Lesions	Management/Next Dose of Nivolumab ± Ipilimumab
≤ Grade 1	No change in dose*
Grade 2	Continue protocol therapy*; Topical steroids do not require protocol therapy discontinuation. If prolonged symptoms require systemic corticosteroids, decisions regarding whether protocol therapy may be reinstated following weaning of immunosuppression must be made in consultation with Protocol Chair/Vice-Chair and DVL Leadership.

Skin Rash and Oral Lesions	Management/Next Dose of Nivolumab ± Ipilimumab
Grade 3	Hold* until ≤ Grade 1; if resolves within 7 days, then resume at same dose level. Topical steroids do not require protocol therapy discontinuation. If prolonged symptoms require systemic corticosteroids, decisions regarding whether protocol therapy may be reinstated following weaning of immunosuppression must be made in consultation with Protocol Chair/Vice-Chair and DVL Leadership.
Grade 4	Discontinue therapy, Systemic corticosteroids indicated.
*Patients with purpuric or bullous lesions must be evaluated for vasculitis, Steven-Johnson syndrome, TEN, and autoimmune bullous disease including oral lesions of bullous pemphigus/pemphagoid. Pruritus may occur with or without skin rash and should be treated symptomatically if there is no associated liver or GI toxicity. Note skin rash typically occurs early and may be followed by additional events particularly during steroids tapering.	
Recommended management: See Skin AE Management Algorithm	

6.4.1 **BMS Recommended Skin Adverse Management Algorithm**

These suggested management guidelines are taken from the BMS algorithms provided in the Investigator's Brochure.

Toxicity (CTCAE v.5)	Management	Follow-up
Grade 1/2 Rash	
 
• Symptomatic therapy (e.g. antihistamines, topical steroids)
 
• Continue protocol therapy
 
	
If persists > 1-2 weeks or recurs:
 
 
• Consider skin biopsy
 
• Hold protocol therapy
 
• Consider 0.5-1 mg/kg/day methylprednisolone IV or oral equivalent
 
• Once improving, taper steroids over at least 1 month
 
• Consider prophylactic antibiotics for opportunistic infections
 
 
If worsens: Treat as Grade 3/4

Grade 3/4 Rash	
 
• Hold infusion
 
• Consider skin biopsy
 
• Dermatology consult
 
• 0.5-1 mg/kg/day methylprednisolone IV or IV equivalent
 
	
If improves to Grade 1:
 
 
• Taper steroids over at least 1 month,
 
• Add prophylactic antibiotics for opportunistic infections
 

Patients on IV steroids may be switched to an equivalent dose of oral corticosteroids (e.g. prednisone) at start of tapering or earlier, once sustained clinical improvement is observed. Lower bioavailability of oral corticosteroids should be taken into account when switching to the equivalent dose of oral corticosteroids.

6.5 **Dose modifications for Hepatic/Pancreatic Adverse Events**

Liver Function Elevation	Management/Next Dose of Nivolumab ± Ipilimumab
≤ Grade 1	Continue protocol therapy
Grade 2	Hold until baseline. If resolves within 7 days, resume at same

Liver Function Elevation	Management/Next Dose of Nivolumab ± Ipilimumab
	dose level.
Grade 3	Off protocol therapy unless DLT exception in Section 5.4.1 is met.
Grade 4	Off protocol therapy unless DLT exception in Section 5.4.1 is met.
See Appendix IX for values that represent thresholds between CTCAE grades. Continued treatment of active immune mediated hepatitis may exacerbate ongoing inflammation. Holding drug to evaluate LFT changes and early treatment are recommended.	
LFT changes may occur during steroid tapers from other events and may occur together with other GI events including cholecystitis/pancreatitis.	
Recommended management: see for Hepatic AE management algorithm	

Pancreatitis; Amylase/Lipase	Management/Next Dose of Nivolumab ± Ipilimumab
≤ Grade 1	Continue protocol therapy
Grade 2 Amylase	Continue protocol therapy
Grade 2 Pancreatitis/Lipase	Hold until resolution to ≤ Grade 1; Resume at same dose level if asymptomatic
Grade 3	Off protocol therapy unless DLT exception in Section 5.4.1 is met.
Grade 4	Off protocol therapy
Patients may develop symptomatic and radiologic evidence of pancreatitis as well as DM and DKA. Lipase elevation may occur during the period of steroid withdrawal and with other immune mediated events or associated with colitis, hepatitis, and patients who have asymptomatic lipase elevation typically have self-limited course and may be retreated. For treatment management of symptomatic pancreatitis please follow the Hepatic Adverse Event Management Algorithm below	

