A cycle may be repeated every 28 days for Parts A and B (and either every 21 days or 28 days for Parts C, D, and E) if the patient has again met the parameters as defined in the eligibility section, [Section 4.0](#), has not met any of the criteria for removal from therapy per [Section 10.1](#), and has not experienced a dose-limiting toxicity. A delay of up to 7 days from the date of the next scheduled treatment dose may be allowed. Please note the following exceptions:

- Patients may continue on to the next cycle if Pancreatic Function is  $\leq$  Grade 1 (See [Section 6.5](#))
- Patients who experience pleural effusion may continue onto the next cycle upon resolution as per [Section 6.8](#).

5.3 **Grading of Adverse Events**

Adverse events (toxicities) will be graded according to the NCI Common Terminology Criteria for Adverse Events (CTCAE) version 5.0. All appropriate treatment areas should have access to a copy of the CTCAE version 5.0. A copy of the CTCAE version 5.0 can be downloaded from the CTEP web site [http://ctep.cancer.gov/protocolDevelopment/electronic\\_applications/ctc.htm](http://ctep.cancer.gov/protocolDevelopment/electronic_applications/ctc.htm). Any suspected or confirmed dose-limiting toxicity should be reported immediately (within 24 hours) to the Study Chair.

5.4 **Definition of Dose-Limiting Toxicity (DLT)**

DLT will be defined as any of the following events that are possibly, probably, or definitely attributable to protocol therapy. DLT definitions will be the same for all parts. The DLT

observation period for the purposes of dose-escalation in Part C or dose de-escalation in Part A will be the first cycle of therapy. Toxicities with subsequent cycles will be monitored carefully and if significant numbers of delayed toxicities are observed, consideration will be given to a protocol amendment to focus on delayed toxicities in assessing the MTD.

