### 6.10 Dose Modifications for Neurologic Adverse Events

Neurologic events	Management/Next Dose of Nivolumab ± Ipilimumab
≤ Grade 1	Continue protocol therapy*
Grade 2	Hold until resolution to baseline.* Resume with no change in dose.*
Grade 3	Off protocol therapy
Grade 4	Off protocol therapy

\*Patients with any CNS events including aseptic meningitis, encephalitis, symptomatic hypophysitis, or myopathy, peripheral demyelinating neuropathy, cranial neuropathy (other than peripheral n. VII), GB syndrome, myasthenia gravis should be taken off protocol therapy.  
Recommended management: See Neurologic Adverse Event Management Algorithm below

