#### 6.10.1 BMS Recommended Neurologic Adverse Event Management Algorithm

These suggested management guidelines are taken from the BMS algorithms provided in the Investigator's Brochure.

Toxicity (CTCAE v.5)	Management	Follow-up
Grade 1 Neurological Toxicity	
 
Continue protocol therapy
 
	
 
Continue to monitor the patient
 
 
If worsens:
 
 
Treat as Grade 2 or 3/4
 

Grade 2* Neurological Toxicity	
 
Hold infusion
 
Treat symptoms per local guidelines
 
Consider 0.5 to 1 mg/kg/day methylprednisolone IV or oral equivalent
 
	
If improves to baseline:
 
 
within 7 days resume protocol therapy, if persists >7 days discontinue protocol therapy
 
 
If worsens:
 
 
Treat as Grade 3/4
 

Toxicity (CTCAE v.5)	Management	Follow-up
Grade 3/4 Neurological Toxicity**	
 
Discontinue protocol therapy
 
Obtain neurology consult
 
Treat symptoms per local guidelines
 
1-2 mg/kg/day methylprednisolone IV or IV equivalent
 
Add prophylactic antibiotics for opportunistic infections
 
	
If improves to Grade 2:
 
 
Taper steroids over at least 1 month
 
 
If worsens or atypical presentation:
 
 
Consider IVIG or other immunosuppressive therapies per local guidelines
 

\* Patients with any CNS events including aseptic meningitis, encephalitis, symptomatic hypophysitis, or myopathy, peripheral demyelinating neuropathy, cranial neuropathy (other than peripheral n. VII), GB syndrome, myasthenia gravis should be taken off protocol therapy.

\*\* With the exception of decreased tendon reflex (DTR); any grade of DTR does not require a dose modification.

Patients on IV steroids may be switched to an equivalent dose of oral corticosteroids (e.g. prednisone) at start of tapering or earlier, once sustained clinical improvement is observed. Lower bioavailability of oral corticosteroids should be taken into account when switching to the equivalent dose of oral corticosteroids.

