#### 6.11 Dose Modifications for Endocrine Adverse Events

Endocrine Hypophysitis; Adrenal Insufficiency	Management/Next Dose of Nivolumab ± Ipilimumab
≤ Grade 1	Continue protocol therapy; See Endocrine Management Algorithm
Grade 2	Off protocol therapy if DLT criteria in Section 5.4.1 is met.
Grade 3	Off protocol therapy
Grade 4	Off protocol therapy

Note all patients with symptomatic pituitary enlargement, exclusive of hormone deficiency, but including severe headache or enlarged pituitary on MRI should be considered grade 3 events. Isolated thyroid or testosterone deficiency may be treated as grade 2 if there are no other associated deficiencies and adrenal function is monitored. Please evaluate pituitary function before beginning steroid therapy or replacement therapy of any kind.
	
Recommended management: See Endocrine Management Algorithm	

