#### Skin Related Toxicity

For skin-related Grade 3 autoimmune toxicity lasting > 7 days or Grade 4 autoimmune toxicity, including severe generalized pruritis or rash, symptomatic treatment will be given and patients will be removed from protocol therapy. Therapy will be as clinically indicated and may include local skin care, antihistamines, or corticosteroids (which can be local/topical or systemic). The use of topical corticosteroids for grades 1 -3 dermatitis will be allowed, and will not require patients to be removed from study. In the case of late-occurring hypersensitivity symptoms (e.g., appearance within one week after treatment of a localized or generalized pruritis), symptomatic treatment may be given (e.g., oral antihistamine, topical steroids for the skin). A dermatologist should evaluate persistent (lasting >7 days) and/or severe rashes or pruritus. A biopsy should be performed if appropriate and photos should be obtained.

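### Section 6.4 leaves re-treatment open after steroid-treated rash that 5.2, and for prolonged Grade 3 also 7.3, rules out; 6.10 and 6.10.1 differ on Grade 2 neurologic events

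*Combined protocol and SAP*

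**What the plan says.** **Rash.** In the 6.4 table, the Grade 2 and Grade 3 rows both say that if prolonged symptoms need systemic corticosteroids, "decisions regarding whether protocol therapy may be reinstated following weaning of immunosuppression must be made in consultation with Protocol Chair/Vice-Chair and DVL Leadership". The skin paragraph of 7.3 has a narrower trigger, "For skin-related Grade 3 autoimmune toxicity lasting > 7 days or Grade 4 autoimmune toxicity", and a firm outcome: "symptomatic treatment will be given and patients will be removed from protocol therapy". Section 5.2 makes a further cycle conditional on the patient again meeting the eligibility parameters "and has not experienced a dose-limiting toxicity", and adds: "A delay of up to 7 days from the date of the next scheduled treatment dose may be allowed". Its listed exceptions are pancreatic function and pleural effusion. Section 6.2 removes patients with a non-hematological DLT, subject to exceptions in 6.3 to 6.12.

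**Neurologic, Grade 2.** The 6.10 table reads "Hold until resolution to baseline", then resume at the same dose. The 6.10.1 algorithm allows a patient who improves to baseline "within 7 days resume protocol therapy" and discontinues if the event persists for more than 7 days.

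**Lesser mismatches.** For Grade 4 rash, 6.4 discontinues therapy, while 6.4.1 groups Grade 3 and 4 under holding the infusion. For the pituitary, the note in 6.11 says that symptomatic enlargement, "including severe headache or enlarged pituitary on MRI should be considered grade 3 events", and Grade 3 is off protocol therapy; the 6.10 footnote also takes symptomatic hypophysitis off. Section 6.11.1 says only to hold the infusion, give steroids and start hormone therapy.

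**The concern.** These sections decide whether a child who has had an immune-related event receives the drugs again. If they give different answers, the outcome can turn on which section is consulted. That is first a safety matter. It also makes time on therapy, and the reasons recorded for stopping it, less comparable between patients in a part that may have only 10 to 20 evaluable children. Part E is the part not marked as completed in Section 5.1, and it uses ipilimumab at 3 mg/kg.

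**Working it through.** The plan states no figure that depends on this point, so there is none to reproduce. The check is a cross-reading followed by a count of days.

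**Step 1. Are these rashes DLTs?** Under 5.4.1, Grade 3 rash escapes DLT status only if it resolves to Grade 1 or less within 7 days, so prolonged Grade 3 rash is a DLT. Grade 2 non-hematological toxicity needing systemic immunosuppression is also a DLT, and rash is not among its exclusions.

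**Step 2. Outcome by section.**

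| Event | 6.4 | 7.3 | 5.2 | 6.2 |
|---|---|---|---|---|
| Grade 3 rash over 7 days, systemic steroids | Re-treatment open, by consultation | Removed | Next cycle barred (DLT) | Removal subject to 6.4 |
| Grade 2 rash, systemic steroids | Re-treatment open, by consultation | Not covered | Next cycle barred (DLT) | Removal subject to 6.4 |

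Section 6.4 therefore agrees with 6.2, but not with 5.2 in either row, nor with 7.3 in the first. The carve-out in 6.2 is attached to its own removal sentence. It does not amend 5.2, which has a separate exception list, or 7.3. Section 10.1(c) refers to both 5.4 and 6.0, so it does not settle the matter.

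**Step 3. Can the 6.4 route be used within the timing in 5.2?**
- Longest gap between doses under 5.2 = dosing interval + 7 days. Parts C to E, cycles 1-4: 21 + 7 = 28 days. Every-14-day dosing: 14 + 7 = 21 days.
- Shortest time from steroid start to re-dosing = taper + steroid-free period. The taper in 6.4.1 is at least 1 month. The steroid-free period in 4.2.2.1, if re-applied through 5.2, is 7 days (14 days where steroids were given for immune events of prior therapy).
- Assumptions, all favorable to re-dosing: 1 month = 28 to 31 days, no days on steroid before the taper, and steroids started on the day of the last dose.
- With 7 days: 28 + 7 = 35 to 31 + 7 = 38. With 14 days: 28 + 14 = 42 to 31 + 14 = 45. None fits within 28 or 21.
- With no steroid-free period, only a 28-day taper on the 21-day schedule fits, exactly (28 = 28).

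So a site that follows the suggested taper cannot use the 6.4 route within 5.2, even leaving the DLT bar aside, except in that single case.

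**Step 4. Grade 2 neurologic events.** Section 6.10 alone has no limit, but 5.2 caps the delay at 7 days from the next scheduled dose, and 5.4.1 makes a delay of more than 7 days a DLT. The algorithm's 7 days refer to persistence of the event. Illustration: an event from Day 2 to Day 20 of a 21-day cycle lasts 20 - 2 = 18 days and delays no dose, since the next is due on Day 22. Section 6.10 resumes and the delay limit in 5.2 is met; 6.10.1 discontinues. If the same event began when a dose was due, the delay would exceed 7 days: 6.10 would still resume, while 5.2 and 6.10.1 would not.

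**Step 5. Effect on DLT counts.** DLT status comes from 5.4.1, whichever re-treatment text is followed. The DLT count, and the Part E rule of one Cycle 1 DLT in the first 10 patients or 4 in 20, are unchanged.

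**The case against.** The best defense is that the protocol has safeguards. Section 6.4 gives the rash decision to the study leadership, not the site. Suspected DLTs go to the Study Chair within 24 hours, dosage modifications must be notified, and evaluations are reviewed weekly. Section 6.2 expressly allows 6.4 to depart from removal. The algorithms are labeled as suggested. Tumor evaluation is still required about 100 days after the last dose. Much of this stands, and it limits how far handling can drift between sites. It does not remove the conflict: 7.3 and 5.2 offer no consultation route for rash, no order of precedence is stated, and the main rash conflict does not involve an algorithm.

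Several stronger readings are tempting but unsupported:
- A reader might infer that 7.3 removes every child with steroid-treated rash. It covers only Grade 3 beyond 7 days and Grade 4.
- A reader might infer that 5.2 removes the child. It withholds the next cycle.
- A reader might infer one pattern across organ systems. The neurologic table is looser than its algorithm; the pituitary table is stricter.
- A reader might see direct contradictions on Grade 4 rash and pituitary disease. The algorithms say to hold but never to resume, and the 6.11.1 row covers symptomatic endocrinopathy generally, so a hold can be read alongside removal.

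**Conclusion.** The contradiction is real for prolonged Grade 3 rash treated with systemic steroids (6.4 against 7.3 and 5.2) and for Grade 2 rash needing systemic steroids (6.4 against 5.2 only). Grade 2 neurologic events carry a separate inconsistency about whether a 7-day limit applies and what it is counted from. The Grade 4 rash and pituitary entries are lesser mismatches of wording.

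The consequence is uncertainty over re-exposure and uneven handling; no error rate, power or sample size changes. The day counts rest on following the suggested taper and on 5.2 re-applying the steroid-free period. The DLT bar in 5.2 needs neither assumption.

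A reader might want a probability that some child meets the conflict. The documents do not support one. They give no rate for prolonged Grade 3 or steroid-requiring rash. The above-20% listing for ipilimumab is for maculo-papular rash as such, Section 2.4 reports less rash in children than in adults, and Part E reaches 20 evaluable patients only if stage 2 opens.

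**What to change.** The sponsor's clinicians should reconcile the following so that each event has one stated outcome wherever it appears:
- Rash: 5.2, 6.2, 6.4, 6.4.1 and 7.3, for prolonged Grade 3, steroid-treated Grade 2, and Grade 4.
- Grade 2 neurologic events: 6.10 and 6.10.1, with the delay limits in 5.2 and 5.4.1, stating what any 7-day limit is counted from.
- Symptomatic pituitary disease: 6.11, 6.11.1 and the 6.10 footnote.

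Any intended exception should be added to the list in 5.2, covering both the DLT condition and the delay limit. Where none is intended, the text that implies one should be changed. A blanket sentence giving tables precedence over algorithms is not advised: it would settle the Grade 2 neurologic outcome by default, and that is a clinical decision. No view is given here on which rule is right.

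The cost is wording in a small number of table cells and paragraphs in the next amendment. Sample size, stopping rules and analyses do not change.

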6.5.1 BMS Recommended Hepatic Adverse Event Management Algorithm

These suggested management guidelines are taken from the BMS algorithms provided in the Investigator’s Brochure.

Consider imaging for obstruction.

Toxicity (CTCAE v.5)	Management	Follow-up
Grade 1* AST or ALT, and/or bilirubin increased	
 
Continue protocol therapy
 
	
 
Continue routine LFT monitoring per Table 8.1
 
 If worsens: 
 
Treat as Grade 2 or 3/4
 

Toxicity (CTCAE v.5)	Management	Follow-up
Grade 2* AST or ALT, and/or bilirubin increased	
 
• Hold infusion
 
• Increase LFT monitoring to every 3 days
 
	
If improves to baseline:
 
 
• Continue routine LFT monitoring per Table 8.1
 
• Resume protocol therapy
 
 
If elevations persist >5-7 days or worsen:
 
 
• 0.5-1 mg/kg/day methylprednisolone IV or oral equivalent
 
• When LFT returns to grade 1 or baseline, taper steroids over at least 1 month
 
• Consider prophylactic antibiotics for opportunistic infections
 

Grade 3 or 4* AST or ALT, and/or bilirubin increased	
 
• Discontinue protocol therapy
 
• Increase LFT monitoring to every 1-2 days
 
• 1-2 mg/kg/day methylprednisolone IV or oral equivalent**
 
• Add prophylactic antibiotics for opportunistic infections
 
• Consult gastroenterologist
 
	
If improves to Grade 2:
 
 
• Taper steroids over at least 1 month
 
 
If does not improve in > 3-5 days, worsens or rebounds:
 
 
• Add mycophenolate mofetil 600 mg/m^2/dose (max 1 g/dose) BID
 
• If no response within an additional 3-5 days, consider other immunosuppressants per local guidelines
 

Patients on IV steroids may be switched to an equivalent dose of oral corticosteroids (e.g. prednisone) at start of tapering or earlier, once sustained clinical improvement is observed. Lower bioavailability of oral corticosteroids should be taken into account when switching to the equivalent dose of oral corticosteroids.

\*See [Appendix IX](#) for values that represent thresholds between CTCAE grades.

\*\* The recommended starting dose for Grade 4 Hepatitis is 2 mg/kg/day methylprednisolone IV.

